Data Analysis for Drug Repurposing for Effective Alzheimer's Medicines – Propranolol/Carvedilol vs Atenolol/Bisoprolol/Sotalol

NCT05794997

July 7, 2023

1. Comparison Details

a. Intended aim(s)

To evaluate the comparative risk of dementia onset between patients treated with Propranolol or Carvedilol versus Atenolol, Bisoprolol, Sotalol for hypertension.

b. Primary endpoint

Incident dementia (i.e., Alzheimer's disease, vascular dementia, senile, presenile, or unspecified dementia, or dementia in other diseases classified elsewhere).

2. Person responsible for implementation of replication in Action

[name]

3. Data Source(s)

Medicare, 2008-2019

4. Study Design Diagrams

[figure not shown]
[figure not shown]

Figure- Alternate analysis approaches

■■■ Included person-time
■■■ Excluded person-time

5. Cohort Identification

a. Cohort Summary

This study will employ a new user, active comparator, observational cohort study design comparing Propranolol or Carvedilol to hydrochlorothiazide. The patients will be required to have continuous enrollment during the baseline period of 365 days before initiation of Propranolol or Carvedilol or Atenolol, Bisoprolol or Sotalol (index date). Follow-up for the outcome (dementia) differs between analyses. Follow-up begins the day after drug initiation (analysis 1, 3, 4); 180 days after drug initiation (analysis 2).

b. Key details regarding cohort creation

Index date:

- Day of initiation of new Propranolol or Carvedilol or Atenolol, Bisoprolol or Sotalol use

Inclusion criteria for analyses 1, 3, 4:

- Aged \geq 65 years on the index date
- 365 days enrollment in Medicare Parts A, B, and D with no HMO coverage
- No use of Propranolol, Carvedilol, Atenolol, Bisoprolol, Sotalol any time prior to index date (all available lookback approach with a minimum of 365 days)
- No use of Propranolol, Carvedilol and Atenolol, Bisoprolol, Sotalol concomitantly on index date
- No diagnosis of dementia any time prior to and including index date
- At least 1 inpatient claim or 2 outpatient claims with hypertension diagnosis recorded in 365 days prior to index date

Inclusion criteria for analysis 2:

- Aged \geq 65 years on the index date
- 365 days enrollment in Medicare Parts A, B, and D with no HMO coverage
- No use of Propranolol, Carvedilol, Atenolol, Bisoprolol, Sotalol any time prior to index date (all available lookback approach with a minimum of 365 days)

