Anti-epileptic mood stabilizers	Lipid lowering drugs
Anti-epileptics (other than mood stabilizers)	Non-insulin diabetes medications
Atypical antipsychotics	Insulin
Benzodiazepines	Antidepressants
Serotonin-norepinephrine reuptake Inhibitors	Typical antipsychotics
Selective serotonin reuptake inhibitors	Anticoagulants
Tricyclic antidepressants (TCAs)	Antiplatelet agents

Comorbid conditions	
Atrial fibrillation	Chronic liver disease
Coronary artery disease	Asthma
Heart failure	Ischemic heart disease
Stroke or transient ischemic attack	Chronic obstructive pulmonary disease
Peripheral vascular disease	Malignancy
Hyperlipidemia	Drug or alcohol abuse or dependence
Renal dysfunction	Venous thromboembolism

ICD-9, ICD-10, HCPCS, and NDC codes used to define the covariates listed above are available in Appendix A.

c. Outcome variables and study follow-up:

- **Primary outcome:** incident dementia, i.e., Alzheimer's disease, vascular dementia, senile, presenile, or unspecified dementia, or dementia in other diseases classified elsewhere. Outcome will be defined by 1 inpatient claim or 2 outpatient claims in analysis 1, 2, 3. In analysis 4, the outcome will be defined by 1 inpatient or 1 outpatient claims and 1 prescription claim for a symptomatic treatment [donepezil, galantamine, rivastigmine, and memantine] within 6 months of each other with outcome date assigned to second event in the sequence.

- Secondary outcomes: Individual component:
Alzheimer's disease

Condition	ICD-9 and ICD-10 codes
Alzheimer's disease	331.0*, F00*, G30*
Vascular dementia	290.4*, F01*
Senile, presenile, or unspecified dementia	290.0*, 290.1*. 290.3*, 797*, F03*
Dementia in other diseases classified elsewhere	331.1*, 331.2*, 331.7*, 294.1*, F02*

For analysis 1,3, and 4 the follow-up will start the day after initiation of Propranolol or Carvedilol and Atenolol, Bisoprolol or Sotalol and will continue until the earliest date of the following events:

- The first occurrence of the outcome of interest
- The date of end of continuous registration in the database,
- End of the study period,
- Measured death event occurs,
- The date of drug discontinuation, defined as the date of the last continuous treatment episode of the index drug (Propranolol or Carvedilol and hydrochlorothiazide) plus a defined grace period (i.e., 90 days after the end of the last prescription's days' supply in main analyses).

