Peripheral vascular disease	129,600 (22.2%)	40,710 (17.4%)	0.12	39,670 (17.9%)	39,327 (17.7%)	0.01
Renal dysfunction	236,212 (40.5%)	56,863 (24.4%)	0.35	56,068 (25.3%)	56,128 (25.3%)	0.00
Stroke or transient ischemic attack	68,173 (11.7%)	23,278 (10.0%)	0.05	22,586 (10.2%)	22,216 (10.0%)	0.01
Venous thromboembolism	37,549 (6.4%)	11,617 (5.0%)	0.06	11,391 (5.1%)	11,122 (5.0%)	0.00

9. Statistical analysis plans

Incidence rates for the outcome will be estimated for the treatment and reference groups before and after PS matching. The competing risk of death could be of concern for the current set of analyses if mortality is frequent among patients included in the cohort and if differences in the risk of mortality between treatment and reference groups are substantial. In the PS-matched sample, we will use cause-specific hazard models⁷ to provide hazard ratios averaged over the entire follow-up period as well as interval specific hazard ratios (1, 2, and 3 years) for the association between the treatment of interest and risk of ADRD after considering all-cause mortality as a competing event. Pre-specified subgroup analyses will be conducted based on age, sex, and baseline cardiovascular disease. In addition to the Medicare dataset, we will pursue a similar analysis within Clinical Practice Research Datalink (CPRD), a UK population health dataset, to validate our results.

10. References

4. Austin PC. Some Methods of Propensity-Score Matching had Superior Performance to Others: Results of an Empirical Investigation and Monte Carlo simulations. *Biometrical Journal*. 2009;51(1):171-184.

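### Section 5b excludes prior dementia diagnoses but not prior fills of the four dementia drugs that the analysis 4 outcome uses, with a claim, as evidence of dementia

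*Combined protocol and SAP*

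**What the plan says.** Section 5b has two eligibility lists, one for analyses 1, 3 and 4 and one for analysis 2. Both carry the same dementia criterion: "No diagnosis of dementia any time prior to and including index date". Neither mentions a dementia drug. Both require "365 days enrollment in Medicare Parts A, B, and D with no HMO coverage", so pharmacy fills before index are visible for at least a year.

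Section 6c sets two outcome definitions.

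- Analyses 1-3: "Outcome will be defined by 1 inpatient claim or 2 outpatient claims in analysis 1, 2, 3".
- Analysis 4: "In analysis 4, the outcome will be defined by 1 inpatient or 1 outpatient claims and 1 prescription claim for a symptomatic treatment". The drugs and timing are given as "donepezil, galantamine, rivastigmine, and memantine] within 6 months of each other with outcome date assigned to second event in the sequence".

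The four drugs appear nowhere else. They are not in the covariate list (section 6b) or the balance table (section 8).

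The flowchart in section 5c has a row labelled 'Dementia Exclusion' (-55,850) with no definition. The next row removes 46,478 patients for nursing home admission, a criterion that section 5b does not list.

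**The concern.** The endpoint is incident dementia. A patient already dispensed one of these drugs, with no dementia code in the available history, may well have had the disease before starting a beta-blocker. The written criteria admit that patient as at risk, and the propensity score has no term for prior use of the drugs.

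Analysis 4 is the most exposed. Its two components may come in either order, and neither is tied to follow-up. A fill before index plus one claim up to six months later, after index, counts as an incident case on the claim date. A continuing user who refills after index also needs only one claim.

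If prior users are equally frequent in both arms and their conversion does not depend on treatment, their events pull the hazard ratio toward 1. If they are unequally frequent, the bias can go either way. The effect is concentrated early, so it would touch the 1-year interval hazard ratio in section 9 more than the ratio averaged over all follow-up.

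**Working it through.** **1. The plan's own figures.** Section 5c: 964,713 - 55,850 = 908,863, as printed; the step removes 55,850 / 964,713 = 5.8% of those reaching it. Next row: 908,863 - 46,478 = 862,385, as printed. The arithmetic is sound, but it does not show whether the dementia step used codes only or codes and fills.

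**2. The text applied to one patient.** Take a donepezil fill two months before index, no prior dementia code, and a first outpatient dementia claim one month after index.

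- Section 5b: eligible.
- Section 6c, analysis 4: fill and claim are three months apart, so the outcome is met on the claim date.
- Section 6c, analyses 1-3: a second outpatient claim is needed, and the fill plays no part.

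Section 6c can also be read as one inpatient claim alone, or one outpatient claim plus a fill. On that reading the analysis 4 point holds for the outpatient route only.

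**3. Size with balanced arms.** The documents give none of these rates, so all are assumptions: prior use p = 0.2%, 0.5% or 1% (888, 2,220 or 4,440 of the 2 × 222,015 = 444,030 matched patients); yearly conversion in prior users c = 10% or 30%; background rate b = 2% a year (analyses 1, 3) or 1% (analysis 4); true hazard ratio 0.80 in other patients and 1 in prior users; no censoring.

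Comparator-arm share of events from prior users: s = pC / (pC + (1-p)B). Observed ratio: 0.80(1-s) + s = 0.80 + 0.20s. In year 1, C = c and B = b. Over three years, C = 1-(1-c)³ and B = 1-(1-b)³.

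Example (analysis 4, year 1, p = 1%, c = 30%): s = 0.0030 / (0.0030 + 0.0099) = 23.3%; ratio 0.80 + 0.20 × 0.233 = 0.847.

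| Analysis, period | c | s at p = 0.2 / 0.5 / 1% | Observed ratio |
|---|---|---|---|
| 1 and 3, year 1 | 30% | 2.9 / 7.0 / 13.2% | 0.806 / 0.814 / 0.826 |
| 1 and 3, year 1 | 10% | 1.0 / 2.5 / 4.8% | 0.802 / 0.805 / 0.810 |
| 1 and 3, three years | 30% | 2.2 / 5.3 / 10.1% | 0.804 / 0.811 / 0.820 |
| 4, year 1 | 30% | 5.7 / 13.1 / 23.3% | 0.811 / 0.826 / 0.847 |
| 4, year 1 | 10% | 2.0 / 4.8 / 9.2% | 0.804 / 0.810 / 0.818 |
| 4, three years | 30% | 4.2 / 10.0 / 18.3% | 0.808 / 0.820 / 0.837 |

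Analysis 2, if patients are also assumed event-free to day 180 (b = 2%, c = 30%, three years): s = 1.9 / 4.5 / 8.7%, ratio 0.804 / 0.809 / 0.817. The delay reduces the effect without removing it.

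**4. Size with unequal arms.** Assume a true ratio of 1.00, c = 30%, comparator prior use 0.5% and treated prior use 0.4% or 0.6%. Year 1, analysis 4:

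- Comparator: 0.005 × 0.30 + 0.995 × 0.01 = 0.01145.
- Treated: 0.004 × 0.30 + 0.996 × 0.01 = 0.01116, or 0.006 × 0.30 + 0.994 × 0.01 = 0.01174.
- Ratios: 0.975 and 1.025.

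For b = 2% they are 0.987 and 1.013. A standardized difference would not flag such an imbalance: 0.001 / √((0.004 × 0.996 + 0.005 × 0.995)/2) = 0.015, and the matched table already reaches 0.02.

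**5. Would a timing rule in 6c do instead?** Suppose both components had to follow index and, as an assumption, 25% of prior users never refill. Without the rule those patients can convert only within six months (1 - 0.7^0.5 = 0.163). For p = 1%, c = 30%, the year 1 share in analysis 4 is 0.01(0.75 × 0.30 + 0.25 × 0.163) = 0.00266, over 0.00266 + 0.0099, or 21.2%. With the rule it is 0.00225 / (0.00225 + 0.0099) = 18.5%. Most of the problem stays, because continuing users refill.

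**The case against.** **The exclusion may already be in place.** The flowchart's dementia row is undefined, and the nursing home row shows that section 5b is not a full record of the steps applied. This stands in part. A reader might infer that the assembled cohort does contain prior users; the documents do not establish that. They show only that the written criteria admit them. Defining the row is therefore the first request.

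**Analyses 1-3 are consistent.** This stands. Eligibility and outcome there both rest on diagnosis claims, and eligibility is the stricter, since any prior diagnosis excludes. A reader might infer that all four analyses contradict themselves; only analysis 4 uses the drugs on one side of index and not the other. For analyses 1-3 the point supports a sensitivity analysis and no more.

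**A fill alone is not dementia, even in 6c.** True: it counts only with a claim, so a prior-fill exclusion will remove some patients who did not have dementia. That is a cost of the fix and does not answer the gap.

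**A separate analysis 4 cohort mixes a cohort change with an outcome change.** Fair, but running analysis 1 with the same exclusion restores the comparison.

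**The model is crude.** It ignores censoring, whereas section 6c censors analyses 1, 3 and 4 at discontinuation plus 90 days. The three-year figures are illustrations.

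**Conclusion.** The point holds as a gap in the written criteria, clearest in analysis 4. The documents give neither the number of uncoded prior users nor their split by arm, so the size is unknown and probably small.

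Under the assumptions shown, a true ratio of 0.80 becomes 0.80-0.83 in year 1 and 0.80-0.82 over three years for analyses 1 and 3, and 0.80-0.85 in year 1 for analysis 4. The upper end needs 1% prior use and 30% conversion together. The assumed imbalance moves a true ratio of 1.00 to about 0.97-1.03 at most.

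The documents do not support a claim that the main result is materially biased. The change is still worth making, because the data are in hand and the early analysis 4 estimates could otherwise carry a non-trivial share of disease that predates exposure.

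**What to change.** 1. Section 5c: define the 'Dementia Exclusion' step, stating whether it uses diagnosis codes only or also fills of the four drugs.
2. If fills are not covered, add to section 5b for analysis 4: no prescription claim for donepezil, galantamine, rivastigmine or memantine on or before the index date, using all available lookback. With the existing diagnosis criterion, this places both analysis 4 components after index, so section 6c needs no separate timing rule.
3. Keep the main cohort for analyses 1-3 and run the same exclusion as a sensitivity analysis. Analyses 1 and 4 can then also be compared in the same cohort.
4. Report the number of prior users by arm, before and after matching, as counts and not only as standardized differences.

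Cost: no new data, since Part D enrollment is already required. Analysis 4 has a slightly smaller cohort and needs its matching and balance table rerun, the other analyses gain a sensitivity analysis, and some excluded patients may not have had dementia.

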- No use of Propranolol, Carvedilol and Atenolol, Bisoprolol, Sotalol concomitantly on index date
- No diagnosis of dementia any time prior to and including index date
- At least 1 inpatient claim or 2 outpatient claims with hypertension diagnosis recorded in 365 days prior to index

DREAM study protocol - Comparison 13 Propranolol or Carvedilol vs Atenolol, Bisoprolol, Sotalol

date

- 180-day continuous use of Propranolol or Carvedilol or Atenolol, Bisoprolol, Sotalol starting on the index date

c. Flowchart of the study cohort assembly

	Less Excluded Patients	Remaining Patients
All patients		27,099,355
Did not meet cohort entry criteria	-20,951,408	6,147,947
Excluded due to insufficient enrollment	-2,442,601	3,705,346
Excluded due to prior use of referent	-1,096,162	2,609,184
Excluded due to prior use of exposure	-1,644,383	964,801
Excluded because patient qualified in >1 exposure category	-88	964,713
Excluded based on Dementia Exclusion	-55,850	908,863
Excluded based on Nursing home admission	-46,478	862,385
Excluded based on Propranolol/Carvedilol OR Atenolol / Bisoprolol / Sotalol Copy	-27,923	834,462
Excluded based on Propranolol / Carvedilol AND Atenolol / Bisoprolol / Sotalol concomitantly on index date Copy	0	834,462
Excluded based on Hypertension: 1 inpatient or 2 outpatient claims within 365 days	-15,211	819,251
Excluded based on Age < 65 years	-1,914	817,337
Final cohort		817,337

6. Variables

a. Exposure-related variables:

Study drug:

The study exposure of interest is initiation of Propranolol or Carvedilol

Comparator:

Initiation of Atenolol, Bisoprolol or Sotalol

b. Covariates:

Demographics	
Age	Region
Gender	Calendar year of index date
Race	Low income subsidy
Dementia risk factors	
Diabetes	Anxiety
Obesity	Bipolar disorder
Coronary artery disease	Schizophrenia
Depression	
Markers for healthy behavior, frailty, healthcare use	
Smoking	Number of hospitalizations
Mammography	Number of physician office visits
Colonoscopy	Number of serum creatinine tests ordered
Fecal occult blood test	Composite frailty score
Influenza vaccination	Number of C-reactive protein tests ordered
Pneumococcal vaccination	Osteoporosis
Herpes zoster vaccination	Fractures

Bone mineral density test	Falls
Number of distinct generic agents	Use of supplemental oxygen
Number of emergency room visits	Combined comorbidity score
Number of outpatient visits	Number of Cardiologist visits

Comedication use	
Lithium	Nitrates

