For analysis 2, the follow-up will start 180 days after initiation of Propranolol or Carvedilol and Atenolol, Bisoprolol or Sotalol and will continue until the earliest date of the following events:

- The first occurrence of the outcome of interest, unless otherwise specified for selected outcomes,
- The date of end of continuous registration in the database,
- End of the study period,
- Measured death event occurs,
- Maximum allowed follow-up time (1095 days) reached

7. Propensity score analysis

We will use a propensity-score (PS)¹-based approach to account for measured confounding in this study. The PS will be calculated as the predicted probability of initiating the exposure of interest (i.e., the repurposing candidate) versus the reference drug conditional on baseline covariates using multivariable logistic regression constructed separately in each data source. On average, patients with similar PSs have similar distribution of potential confounders used to estimate the PS. Therefore, analyses conditioned on the PS provide effect estimates that are free from measured confounding. For all our analyses, initiators of each exposure of interest will be matched with initiators of the reference exposure based on their PS within each data source.² Pair matching will be conducted using a nearest-neighbor algorithm, which seeks to minimize the distance between propensity scores in each pair of treated and reference patients,³ and a caliper of 0.025 on the natural scale of the PS will be used to ensure similarity between the matched patients.⁴

We report multiple diagnostics for PS analysis in this protocol. First, the PS distributional overlap is provided between two groups before and after matching to ensure comparability of these groups.⁵ Next, balance in each individual covariate between two treatment groups is reported using standardized differences.⁶

8. Table for covariate balance

Variable	Crude			PS-Matched		
	Propranolol and Carvedilol (N = 583,870)	Atenolol, Bisoprolol, Sotalol (N = 233,467)	St. Diff	Propranolol and Carvedilol (N = 222,015)	Atenolol, Bisoprolol, Sotalol (N = 222,015)	St. Diff
Demographics						
Age, mean (SD)	75.02 (7.00)	74.75 (6.77)	0.04	74.77 (6.82)	74.75 (6.78)	0.00
Gender, n (%)						
Male	281,232 (48.2%)	97,628 (41.8%)	0.13	93,749 (42.2%)	94,142 (42.4%)	0.00
Female	302,638 (51.8%)	135,839 (58.2%)	-0.13	128,266 (57.8%)	127,873 (57.6%)	0.00
Race, n (%)						

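### Analysis 2 starts follow-up at day 180 but excludes dementia only up to the index date, so patients first diagnosed on days 1–180 enter with dementia and no rule says whether they count as events

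*Combined protocol and SAP*

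**What the plan says.** - Section 5b sets the index date, for every analysis, as the day a study drug is started. It is not moved for analysis 2.
- Section 5b lists separate inclusion criteria for analysis 2. The dementia criterion is identical to that for analyses 1, 3 and 4: "No diagnosis of dementia any time prior to and including index date". The one criterion added for analysis 2 is "180-day continuous use of Propranolol or Carvedilol or Atenolol, Bisoprolol, Sotalol starting on the index date", which does not mention dementia.
- Section 6c: "For analysis 2, the follow-up will start 180 days after initiation of Propranolol or Carvedilol and Atenolol, Bisoprolol or Sotalol". Section 5a gives the same start.
- Section 6c ends analysis 2 follow-up at the earliest of several events. These include "The first occurrence of the outcome of interest, unless otherwise specified for selected outcomes" and "Maximum allowed follow-up time (1095 days) reached". Nothing elsewhere in the document specifies otherwise for any outcome.
- Section 6c, outcome definition: "Outcome will be defined by 1 inpatient claim or 2 outpatient claims in analysis 1, 2, 3". No event date is assigned. A dating rule appears only in the analysis 4 definition, which needs a diagnosis claim and a prescription claim "within 6 months of each other with outcome date assigned to second event in the sequence".
- Section 9 plans hazard ratios over the whole follow-up and for intervals of 1, 2 and 3 years.

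**The concern.** Eligibility is fixed at day 0, while time at risk starts at day 180. The endpoint is incident dementia, so everyone at risk should be free of dementia when follow-up starts. The written criteria do not secure this.

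A patient first diagnosed between days 1 and 180 can be handled in two ways:

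- **Reading A.** Outcome claims are searched from day 180. One later inpatient claim, or two later outpatient claims, makes the patient an incident case.
- **Reading B.** The first occurrence fell before follow-up, so the patient adds no event.

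Two programmers following the same text could produce different event counts. Under reading A, early diagnoses are not removed. They move to just after day 180, which partly undoes the delayed start, one of the main differences between analysis 2 and the analyses that start the day after initiation. The incidence rate rises, and the year-1 interval hazard ratio is affected most.

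A smaller gap concerns an outpatient pair that spans the start of follow-up, for example days 150 and 200. The plan does not say which date is the event date. It also does not say whether a single claim before day 180 counts as a prior diagnosis.

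Analyses 1, 3 and 4 start the day after initiation and are not affected.

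**Working it through.** **Does the gap exist?** Take a patient who starts a study drug on day 0, is first diagnosed on day 90 and uses the drug continuously to day 180.

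1. Dementia up to and including day 0: none, so the patient is eligible.
2. Continuous use for 180 days: met.
3. Follow-up starts on day 180, with dementia present for 90 days.
4. No other criterion or end-of-follow-up rule refers to days 1–180.

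The flowchart in section 5c does not settle the matter. It has one dementia step, but it also has no 180-day-use step, so it does not describe the analysis 2 cohort.

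**How large could it be under reading A?** The plan states no dementia rate, event count or power figure, so there is no planned figure to reproduce. Inputs from the plan are the 180-day gap, the 1095-day maximum and the 1- and 2-year intervals. Assumed inputs are a constant rate λ of 0.01–0.03 per year, a proportion r of early cases that meet the outcome definition again after day 180, and no other censoring.

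Share of counted events that are early cases = r·p / (r·p + q), with p = 1 − exp(−λ·180/365.25) and q = 1 − exp(−λT).

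- λ = 0.01: p = 0.004916; q = 0.009943 (365 days), 0.019801 (2 years), 0.029535 (1095 days).
- λ = 0.03: p = 0.014676; q = 0.029535, 0.058235, 0.086013.

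| Window | Lower end (λ = 0.01, r = 0.8) | Upper end (λ = 0.03, r = 1) |
|---|---|---|
| Year 1 | 0.003933/(0.003933 + 0.009943) = 28.3% | 0.014676/(0.014676 + 0.029535) = 33.2% |
| 2 years | 0.003933/(0.003933 + 0.019801) = 16.6% | 0.014676/(0.014676 + 0.058235) = 20.1% |
| 1095 days | 0.003933/(0.003933 + 0.029535) = 11.8% | 0.014676/(0.014676 + 0.086013) = 14.6% |

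With r = 0.5 the shares are 19.8–19.9% in year 1 and 7.7–7.9% over 1095 days. Under reading B the share is 0%.

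**Effect on the hazard ratio under reading A.** It is approximated by the ratio of event rates. The reference rate is λ throughout. The treated rate is λ × early HR to day 180 and λ × 0.90 afterwards. Early cases that qualify again are assumed to contribute 60 days. In each arm, events = r·p + (1 − p)·q and person-years = r·p·60/365.25 + (1 − p)·q/(later rate).

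Example: year 1, λ = 0.02, r = 1, early HR 1.2.

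- Treated: p = 0.011758, q = 0.017827; events 0.029375; person-years 0.980668; rate 0.029954.
- Reference: p = 0.009808, q = 0.019788; events 0.029402; person-years 0.981303; rate 0.029962.
- Ratio = 0.029954/0.029962 = 1.00, against a later HR of 0.90.

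Over λ 0.01–0.03 and r 0.8–1.0:

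| Early HR | 1095 days | Year 1 |
|---|---|---|
| 0.9 | 0.90 | 0.90 |
| 1.0 | 0.91 | 0.93 |
| 1.2 | 0.94 | 0.99–1.00 |
| 1.5 | 0.97–0.99 | 1.07–1.10 |

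**Number of patients.** The matched cohort in section 8 is 2 × 222,015 = 444,030. If all of them met the 180-day-use criterion, 444,030 × p gives 2,183 (λ = 0.01) to 6,516 (λ = 0.03) first diagnosed on days 1–180. The size of the analysis 2 cohort is not given, so the true number would be smaller.

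**The case against.** The strongest reply is that the text leans towards reading B. The endpoint is incident dementia and follow-up ends at its first occurrence. For a diagnosis on day 90 that date precedes the start of follow-up, so the patient has no time at risk. It is fair that an early diagnosis would not be counted at its own date. The text still does not say whether the patient is removed, stays at risk with no possible event, or becomes an event at the next qualifying claims. A search for outcome claims from day 180 would produce the last of these unless a filter stops it.

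Second, the design diagrams in section 4 are not shown in the text available and may depict an exclusion window to day 180. That cannot be ruled out. If they do, the written criterion disagrees with them and needs the same edit.

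Third, the sizes rest on assumed rates, re-qualification proportions and hazard ratios. This stands: they show scale only, and the direction of any bias in the hazard ratio cannot be determined from the documents.

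Fourth, the plan does not state the purpose of the day-180 start, which may simply mark completion of the use criterion. Prevalent cases at time zero would still conflict with an incident endpoint.

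Fifth, a two-claim definition is naturally dated at the second claim, and the missing rule is common to analyses 1–3. This is largely right and makes the dating point the minor part. Finally, only one of four analyses is affected, and the plan does not name it as primary.

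**Conclusion.** The concern holds on the written criteria. Analysis 2 admits patients who already have dementia when follow-up starts, and the plan does not say what happens to them. The miscounted share of events runs from nothing (reading B) to about one in seven over 1095 days and one in three in year 1 (reading A at the upper assumptions). A hazard ratio shift needs both reading A and an early hazard ratio that differs from the later one; if the two are equal there is no material bias. The point should be fixed before analysis 2 is run, since it bears on a planned estimate and is cheap to settle. That the gap exists in the written text is clear; its size is illustrative.

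**What to change.** In section 5b, for analysis 2 only, require no dementia diagnosis at any time up to and including day 180 after the index date, the start of follow-up. Apply this before the propensity score is estimated and matching is done, so that matched pairs stay intact. State the event date for an outpatient pair that spans day 180, and whether one claim before day 180 is enough to exclude. Show the day-180 exclusions by treatment group in a flowchart for analysis 2, and check that the design diagrams agree.

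The cost is one line of text and one filter. It removes about 0.5–1.5% of patients at the assumed rates (p above). Analysis 2 already selects on continuous use to day 180, so the change adds no new selection time point.

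### The covariates hold no direct marker of pre-dementia cognitive impairment, Parkinson's disease or tremor, so the hazard ratio may partly reflect pre-existing disease if these differ between arms

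*Combined protocol and SAP*

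**What the plan says.** Section 6b groups its covariates under several headings. The one named "Dementia risk factors" holds diabetes, obesity, coronary artery disease, depression, anxiety, bipolar disorder and schizophrenia. Among the comorbid conditions, stroke or TIA is the only neurological disease. The comedication list has antipsychotics, antidepressants, benzodiazepines, anti-epileptics and lithium, but no antiparkinson drug and no anti-dementia drug. The Section 8 table has no row for any of the missing items.

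At entry, Section 5b requires "No diagnosis of dementia any time prior to and including index date". The flowchart in 5c shows 55,850 patients removed at the step "Excluded based on Dementia Exclusion" and 46,478 at "Excluded based on Nursing home admission". The hypertension criterion asks for claims with that diagnosis, not for the reason the drug was prescribed.

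Section 6c states: "For analysis 1,3, and 4 the follow-up will start the day after initiation of Propranolol or Carvedilol". Analysis 2 starts at day 180 and requires 180 days of continuous use. The outcome in 6c includes a category for dementia arising in other diseases (331.1*, 331.2*, 331.7*, 294.1*, F02*). Section 7 says that "analyses conditioned on the PS provide effect estimates that are free from measured confounding".

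**The concern.** Early cognitive impairment and Parkinson's disease can be expected to predict a later dementia code, and claims data can record both. The plan neither excludes nor adjusts for them. A patient with such a condition but no dementia diagnosis can enter the cohort and later count as an event.

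This biases the comparison only if the conditions are unequally distributed between the matched arms. For tremor or Parkinson's disease that is plausible: the study aim is use for hypertension, but hypertension claims in the prior year do not exclude that the drug was started for something else. If the conditions were more frequent in the propranolol/carvedilol arm, the bias would push the HR upward. A repurposing candidate could then look harmful, or a benefit could be hidden. Matching on the listed variables would not reliably remove this, and a large sample would make it look more certain.

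**Working it through.** **Covariate check.** Going through 6b and Section 8 item by item gives no direct marker of cognitive impairment and none of tremor or Parkinson's disease. Appendix A is said to hold codes for the covariates listed in 6b, so it would not add unlisted ones. Analysis 4 uses claims for donepezil, galantamine, rivastigmine and memantine to define the outcome, so these drugs are measurable. Baseline use of them is nevertheless neither excluded nor adjusted for.

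**How much the hypertension step screens.** In the flowchart it removes 15,211 of 834,462 patients, or 1.8%.

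**Possible size.** The plan has no figure to reproduce, and it gives no prevalence of these conditions by arm. For a true HR of 1, the spurious ratio from an omitted binary factor is

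[1 + p1(HR − 1)] / [1 + p0(HR − 1)],

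where p1 and p0 are the prevalences in the exposed and comparator arms and HR is the factor's own hazard ratio for dementia. All inputs below are assumptions.

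| p1 | p0 | HR | Spurious ratio | Standardised difference |
|---|---|---|---|---|
| 2% | 1% | 2 | 1.02/1.01 = 1.010 | 0.08 |
| 3% | 1% | 3 | 1.06/1.02 = 1.039 | 0.14 |
| 5% | 1% | 3 | 1.10/1.02 = 1.078 | 0.24 |
| 10% | 1% | 3 | 1.20/1.02 = 1.176 | 0.40 |

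At 1% versus 0.5% with HR 2 the ratio is 1.01/1.005 = 1.005. The last column is (p1 − p0)/√{[p1(1 − p1) + p0(1 − p0)]/2}. For comparison, the largest crude difference in Section 8 is 0.46 (heart failure), and the largest after matching is 0.02.

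**Random error.** Section 8 gives 222,015 patients per matched arm. The plan states no expected event risk, so I assume 1% to 5%. The 95% half-width on the log scale is 1.96 × √(2/events per arm).

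- 1% risk: 2,220 events per arm; 1.96 × √(2/2,220) = 0.059, about 6%.
- 5% risk: 11,101 events per arm; 1.96 × √(2/11,101) = 0.026, about 2.7%.

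A spurious 1.01 lies inside both intervals. A spurious 1.04 lies inside the first and outside the second. Values of 1.08 and 1.18 lie outside both. With two-sided 0.05 testing, a spurious 1.04 would be declared significant with probability about 0.26 at 1% risk and 0.83 at 5%.

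**The case against.** The strongest reply is that nothing in the documents shows an imbalance. They give no prevalence by arm, no propranolol share of the pooled arm and no prescribing reasons. The crude exposed arm looks cardiac (heart failure 47.9% versus 26.1%), and crude neurological and psychotropic drug use differs little: tricyclics 4.4% in both arms, benzodiazepines 12.8% versus 12.4%, other anti-epileptics 18.6% versus 15.3%. The design uses new users, active comparators and required hypertension claims. It also matches on indirect proxies such as falls and "Composite frailty score", whose components are not given in the text. Section 7 claims freedom from measured confounding only, so it does not overclaim.

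Most of this stands, and it limits the point to a possible bias. It does not close the gap. Balance on proxies does not show balance on tremor or cognitive impairment. The crude cardiac profile also does not describe the matched arm, which keeps 38.0% of exposed patients (222,015 of 583,870) and has heart failure in 27.4%.

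The 180-day start in analysis 2 deserves credit against early reverse causation. It does less against a condition that persists, and no different covariate set is given for that analysis. The figure on alternate analysis approaches is not shown in the available text and its legend includes excluded person-time, so a lag in analysis 3 cannot be ruled out.

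A reader might go further and infer three things that the documents do not support:

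- Pre-existing disease *is* being read as a drug effect. That would need a demonstrated imbalance.
- Early cognitive impairment steers the choice between the two beta-blocker groups. The plan gives no reason why it should, and without imbalance its spurious ratio is 1.00.
- Migraine belongs on the list. The documents contain no link between migraine and dementia.

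**Conclusion.** The omission is a fact of the text; the bias is a possibility. Strong candidate predictors of the outcome that the same claims can measure are left out of the PS, and neither the entry criteria nor analysis 2 fully covers for them. The plan also describes no negative control or quantitative bias analysis that could stand in.

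The size cannot be determined from the documents. Under the assumed inputs it runs from negligible (1.01) to 1.18. The upper end needs a tenfold difference in prevalence, which is far larger than any imbalance left on the measured covariates. The upward direction holds only if the conditions are more common in the exposed arm; for cognitive impairment no direction is established. The check is worth making because it is cheap and either outcome is informative: balance would strengthen the result, and imbalance could prevent a wrong conclusion.

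**What to change.** Add to 6b and to the PS model: baseline codes for mild cognitive impairment or memory loss, baseline use of anti-dementia drugs, Parkinson's disease or parkinsonism, and tremor. Re-match, and show each item in Section 8, where the crude columns will reveal whether there was an imbalance at all. Add a sensitivity analysis of analyses 1 to 4 that excludes patients with any of these codes or drugs in the look-back.

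The cost is a few extra code lists in Appendix A, a PS re-run and re-match in each data source (Medicare, and CPRD for the validation in Section 9), and a slightly smaller sample in the restricted analysis. For Medicare, the data are already held.
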